1.0 PROTOCOL SUMMARY

Postoperative urinary retention (POUR) complicates up to 30% of general abdominal operations. It results in patient discomfort, embarrassment, interference with therapies, and significant nursing burden. More importantly, urinary retention necessitates use of intermittent catheterization or placement of an indwelling urinary catheter, which exposes the patient to an increased risk of urinary tract infection (UTI), urethral injury, and potentially increased hospital length of stay and cost. For these reasons, a safe and effective intervention for preventing POUR would be highly valuable. Despite such a need, no contemporary studies exist evaluating medications that can be used to prevent POUR in broad general surgery populations. To address this gap, we are designing a prospective, randomized, double-blind, placebo-controlled trial to test the hypothesis that preoperative loading with tamsulosin will prevent POUR in patients undergoing elective, inpatient complex intra-abdominal surgery and thereby lead to improved short-term outcomes.

Tamsulosin is a safe and widely-used selective alpha_{1A} adrenergic blocker commonly used for the treatment of lower urinary tract symptoms in men with benign prostatic hypertrophy. It has also been shown to have some benefit in reducing POUR and need for catheterization in men undergoing inguinal hernia repair and other outpatient urologic procedures. To test our hypothesis, we will conduct a randomized, double-blind, placebo-controlled trial in which we administer tamsulosin or placebo for 7 days pre-operatively to patients scheduled for inpatient complex intra-abdominal surgery, and then compare the rates of POUR in each group (Aim 1). We also propose a retrospective analysis of our data to identify risk factors for POUR and subgroups of patients that would derive the greatest benefit from preoperative tamsulosin (Aim 2). Furthermore, we propose to determine if preoperative tamsulosin therapy leads to improved short-term outcomes, including reduced rate of UTI and shorter hospital length of stay (Aim 3).

2.0 INTRODUCTION

Postoperative urinary retention refers to the inability to void spontaneously or completely following surgery. It complicates up to 69% of operations, depending on the type of surgery, and can have significant consequences for the patient.¹ The etiology of postoperative urinary retention is likely multifactorial, with contributing factors including sympathetic stimulation secondary to pain and surgery, local edema, intraoperative bladder distention, patient anxiety, immobilization, damage to parasympathetic nerves of the S2 to S4 dermatome, and medication effects.² It is typically self-limited, and is managed with intermittent or indwelling urinary catheterization until resolution. Multiple risk factors for postoperative urinary retention have been identified. These include opioid use, neuraxial anesthesia, type of operation such as anorectal procedures and lower limb joint arthroplasties, older age, male gender, and pre-existing lower urinary tract symptoms.²

Although an often underemphasized problem following surgery, postoperative urinary retention occurs frequently and can have significant consequences for the patient. Direct effects of urinary retention include patient discomfort, embarrassment, and the consequences of bladder distention such as hemodynamic effects (rarely), prolonged detrusor dysfunction, and possible kidney disease.² Indirect effects of urinary retention are a result of the need for catheterization to empty the bladder. Perhaps the most significant of these is catheter-associated urinary tract infection (CAUTI). UTI is one of the most common hospital-acquired infections, and 70-80% of these are associated with an indwelling

urinary catheter.³ The most important predictor of CAUTI is duration of catheterization, with an estimated 4 to 7% risk of developing bacteriuria for each day of indwelling catheter use.³ Furthermore, indwelling catheters cause gross hematuria and urethral stricture in up to 5% and 7%, respectively, of patients with short-term indwelling urinary catheters.⁴ Concentrated efforts to reduce catheter-associated UTI invariably involve early removal of indwelling urinary catheters (IUC). However, in order to facilitate early catheter removal without a large associated risk of catheter reinsertion, targeted efforts must be made to reduce the risk of urinary retention.

Tamsulosin is a selective alpha-1A adrenoreceptor antagonist that has been demonstrated to be effective in treating lower urinary tract symptoms in men with benign prostatic hypertrophy.⁵ Furthermore, it is a safe and well-tolerated medication with more minimal cardiovascular effects than other less-selective alpha blockers.⁵ It is thought to relieve lower urinary tract symptoms by relaxation of the smooth muscle present in the bladder neck, urethral sphincter, and prostate. Tamsulosin has been studied previously in surgical patients, and was found to reduce the rate of POUR from 21.1% (placebo) to 5.9% in men undergoing varicocelectomy, inguinal hernia repair, and scrotal surgery.⁶ It has not previously been studied in broad general surgery populations, and has not been dosed more than approximately 24 hours pre-operatively. Steady-state concentration of tamsulosin is not achieved until the fifth day of once-daily dosing, which the rationale for the longer preoperative treatment duration this this study.

In summary, POUR is a common, and not inconsequential, complication following general surgery procedures. In particular, it results in the need for catheterization, exposing the patient to all of the concomitant risks. Therefore, the ability to prevent urinary retention, thereby mitigating the need for catheterization, would provide significant benefit to surgical patients.

3.0 STUDY AIMS

In this study, we will test the hypothesis that preoperative loading of the alpha-adrenergic receptor inhibitor tamsulosin will decrease the incidence of postoperative urinary retention in patients undergoing elective complex intra-abdominal surgery, thereby also decreasing the rate of UTI and hospital length of stay. To test this hypothesis, we will accomplish the following aims:

3.1 Specific Aim 1: Determine if tamsulosin administered preoperatively and perioperatively is more effective than placebo in preventing postoperative urinary retention in patients undergoing elective, inpatient, complex intra-abdominal surgery.

We hypothesize that patients treated with tamsulosin for 7 days preoperatively and immediately postoperatively will have a lower incidence of postoperative urinary retention and need for catheterization compared to those patients treated with placebo. To test this hypothesis, we will investigate the following sub-aims:

3.1.1 *Aim 1a.* Determine the frequency of postoperative urinary retention in each group, as defined by need for at least a single intermittent catheterization after surgery or following the removal of IUC.

- 3.1.2 *Aim 1b.* Measure the ability to spontaneously and completely void in patients after the removal of IUC by measuring time until first void, post void residual urine volume, and number of intermittent catheterizations.
- 3.1.3 *Aim 1c.* Determine the rate of IUC replacement.
- 3.1.4 *Aim 1d.* Measure frequency of adverse effects of tamsulosin therapy.
- **3.2 Specific Aim 2:** Identify risk factors for postoperative urinary retention based on preoperative characteristics and type of operation, and identify which patient population benefits the most from preoperative tamsulosin therapy.

We hypothesize that there are identifiable patient- and operation-related characteristics that can predict postoperative urinary retention. In testing this hypothesis, the following two sub-aims will be investigated:

- 3.2.1 *Aim 2a.* Determine what preoperative patient characteristics and operative characteristics predict postoperative urinary retention.
- 3.2.2 *Aim 2b.* Determine which subgroup of patients derives the greatest benefit from preoperative tamsulosin therapy.
- **3.3** Specific Aim 3: Determine if preoperative tamsulosin therapy results in improved short-term outcomes.

In this aim, we will test the hypothesis that reducing the rate of postoperative urinary retention leads to decreased rate of UTI and decreased hospital length of stay. We therefore propose the following sub-aims:

- 3.3.1 *Aim 3a.* Compare and contrast rates of postoperative UTI in patients randomly assigned to tamsulosin therapy compared to those in the placebo arm.
- 3.3.2 *Aim 3b.* Determine postoperative length of stay in the two groups of patients.

3.4 Endpoints

- 3.4.1 Primary endpoint
 - 3.4.1.1 Need for any intermittent catheterization after initial IUC removal
- 3.4.2 Secondary endpoints
 - 3.4.2.1 Need for replacement of IUC
 - 3.4.2.2 Adverse events of tamsulosin and placebo
 - 3.4.2.3 Time from catheter removal, last intermittent catheterization (if performed in the operating room or post-anesthesia care unit), or departure from operating room (if no IUC) until first spontaneous void

- 3.4.2.4 Total number of intermittent catheterizations required per subject
- 3.4.2.5 Post void residual urine volume after first spontaneous void, as measured by bladder scanning
- 3.4.2.6 Need for discharge from the hospital with an IUC
- 3.4.2.7 Urinary tract infection diagnosed within 30 days of operation
 - 3.4.2.7.1 Defined as a symptomatic, culture-confirmed UTI with >10⁵ CFU with a single pathogen if diagnosed while inpatient
 - 3.4.2.7.2 Defined as a subject self-reported, clinician-diagnosed UTI (if diagnosed as an outpatient or at another facility)—to be collected over the phone at 30 day follow up contact with subject
- 3.4.2.8 Hospital length of stay in days

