5.2 Data extraction from medical record

The following information will be extracted from the subject's medical record at the time of preoperative visit, following enrollment in the study: date of birth, age, gender, race, height, weight, information about planned surgery, co-morbidities, past medical history, past surgical history, current medications, allergies, and smoking history. Additional data extracted from the subject's medical record following their operation includes: operation performed, length of operation (minutes), type of anesthesia (general, regional, MAC, local), volume of intravenous fluids administered intra-operatively, estimated blood loss, placement of epidural, type of anesthetic medications used, placement/removal of IUC in the operating room, volume of urine output in the operating room, and whether or not straight catheterization was performed at the conclusion of the case in the operating room.

Data to be extracted from the medical record following discharge from the hospital includes: hospital length of stay (days), whether or not the subject was discharged with an indwelling catheter, diagnosis of urinary tract infection within 30 days of operation, and urine culture data if applicable.

All of the data extracted from a subject's medical record will be entered into the ICTR OnCore Clinical Research Management System.

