10.7 Primary endpoint for interim and final analysis

The primary endpoint for interim and final analysis is need for any intermittent catheterization after initial IUC removal. This outcome will be compared primarily with an intent-to-treat analysis. However, we will also perform an as-treated analysis. Compliance will be measured based on pill-counts. A subject will be considered "compliant" if greater than or equal to 70% of the pills that were supposed to be taken were actually taken.

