10.8 Hypotheses

10.8.1 Primary

10.8.1.1 We hypothesize that subjects treated with tamsulosin will have a decreased need for intermittent catheterization after initial IUC removal compared to those treated with placebo.

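### The primary endpoint counts catheterization only after removal of an indwelling catheter (IUC), so read literally it cannot count retention in a subject who never had one, whereas Aim 1a does

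*Combined protocol and SAP*

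**What the plan says.** All references are to the combined protocol and SAP.

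- **Anchored to IUC removal.** The endpoint list (3.4.1.1) has "Need for any intermittent catheterization after initial IUC removal". Section 10.7 names "need for any intermittent catheterization after initial IUC removal" as the endpoint for both the interim and the final analysis. The primary hypothesis (10.8.1.1) expects a "decreased need for intermittent catheterization after initial IUC removal" on tamsulosin.
- **Broader.** Aim 1a (3.1.1) defines retention as "need for at least a single intermittent catheterization after surgery or following the removal of IUC".
- **No anchor.** Sections 5.5, 10.2 and 10.10 describe the primary outcome as any, or at least one, intermittent catheterization and do not mention an IUC.
- **Subjects with no IUC are foreseen.** The time-to-void endpoint (3.4.2.3) has a separate time origin, "departure from operating room (if no IUC) until first spontaneous void". Sections 4.2.1 and 4.2.2 do not require an IUC.
- **Operating room and PACU.** Section 3.4.2.3 also uses the "last intermittent catheterization (if performed in the operating room or post-anesthesia care unit") as a time origin. Section 5.2 records "placement/removal of IUC in the operating room". The primary endpoint does not mention catheterization in either place.
- **Analysis set.** Section 10.7 states: "This outcome will be compared primarily with an intent-to-treat analysis".

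**The concern.** A subject who never has an IUC has no initial IUC removal. If that subject is later catheterized for retention, the literal endpoint in 10.7 has no way to record an event, while Aim 1a records one. Intent-to-treat keeps the subject in the denominator, so the trial's target outcome would be scored as a non-event. The protocol handles this group for a secondary endpoint but not for the only primary endpoint.

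Timing adds weight. Section 10.5 reports a finding from the interim analysis, which 10.1 and 10.6 describe as unblinded and carried out in May 2016 by the principal investigator and three others. No section says how no-IUC subjects were scored then. If the choice stays open until the final analysis, it could be made by people who have seen outcomes by arm.

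**Working it through.** **1. The definitions side by side, each read literally.**

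| Subject | 3.4.1.1, 10.7, 10.8.1.1 | Aim 1a | 5.5, 10.2, 10.10 |
|---|---|---|---|
| IUC removed on the ward, then intermittent catheterization | event | event | event |
| IUC placed and removed in the operating room, catheterized on the ward | event | event | event |
| Never had an IUC, catheterized on the ward for retention | **cannot be an event** | **event** | **event** |
| IUC removed in the operating room, catheterized in PACU | event | event | event |
| Never had an IUC, catheterized in PACU | **cannot be an event** | **event** | **event** |
| Never had an IUC, straight catheterization in the operating room at the end of the case | cannot be an event | unclear whether this is after surgery | event |

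The definitions disagree only for subjects who never had an IUC. The last row is a further gap that Aim 1a does not close.

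**2. The plan's sample size reproduces.** Inputs from 10.2 and 10.3: 30% vs 15%, two-sided alpha 0.05, power 80%. The mean rate is 0.225.

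- Without continuity correction: n = [1.960 × √(2 × 0.225 × 0.775) + 0.842 × √(0.30 × 0.70 + 0.15 × 0.85)]² / 0.15² = 2.711 / 0.0225 = 120.5, so 121 per arm.
- With continuity correction: (120.5 / 4) × [1 + √(1 + 4 / (120.5 × 0.15))]² = 133.5, so 134 per arm, as stated.
- Exact power at 134 per arm is 80.6% for Fisher's test and 84.7% for the uncorrected chi-squared test.

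The point therefore does not rest on an error in the sample size.

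**3. Events in dispute.** Expected events are 134 × 0.30 = 40.2 on placebo and 134 × 0.15 = 20.1 on tamsulosin. Each 1% of subjects with no IUC puts 0.40 and 0.20 of these in dispute.

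**4. Illustration of power.** The no-IUC share q is an assumption. The illustration takes 30% and 15% to be rates under Aim 1a, the same risk in no-IUC subjects, and the same q in both arms. The literal endpoint then gives rates of 0.30(1 − q) and 0.15(1 − q). Power is by exact enumeration of all 2×2 tables at 134 per arm, two-sided 0.05.

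| Assumed q | Events lost, placebo / tamsulosin | Fisher power | Chi-squared power |
|---|---|---|---|
| 0% | 0 / 0 | 80.6% | 84.7% |
| 2% | 0.8 / 0.4 | 79.5% | 83.8% |
| 5% | 2.0 / 1.0 | 77.8% | 82.3% |
| 10% | 4.0 / 2.0 | 74.8% | 79.6% |
| 20% | 8.0 / 4.0 | 68.1% | 73.5% |

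Under these assumptions the risk ratio stays at 0.50. The risk difference shrinks, for example from 15 to 27 − 13.5 = 13.5 percentage points at q = 10%.

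**The case against.** The strongest reply is that the broad reading is what the authors meant. Aim 1a states it, and 5.5, 10.2 and 10.10 describe the primary outcome without the anchor. The IUC clause may be only a timing rule for subjects who have an IUC, and intent-to-treat would then count the others in the ordinary way. This is plausible, and it stands to this extent: a reader might infer that no-IUC subjects were, or will be, scored as non-events, and the documents do not show that. It does not remove the conflict. The anchored wording sits in the endpoint list, the endpoint for analysis and the primary hypothesis, and the unanchored sections can equally be read as shorthand for it. No section says which governs.

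A reader might also infer a definite loss of power or a bias. The documents do not support that. They give no no-IUC share, and 10.2 links the planned rates to retention as the primary outcome captures it. If 30% and 15% already reflect the narrow wording, nothing is lost.

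A third tempting step is to borrow 3.4.2.3 and rule that a catheterization in the operating room or PACU is not an event. That section only sets a clock for a secondary endpoint. A PACU catheterization after an IUC was removed in the operating room is an event under both the anchored wording and Aim 1a, so such a rule would be a new restriction made after an unblinded look.

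Finally, the start conditions of the bladder management protocol in the appendix do not prove that never-IUC subjects exist. Arriving on the unit without a catheter also covers an IUC removed in the operating room. The evidence is 3.4.2.3.

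**Conclusion.** The point holds as an internal inconsistency in the only primary endpoint, and it should be fixed. Followed literally, 10.7 scores a no-IUC subject catheterized for retention as a non-event, contrary to Aim 1a. Subjects whose IUC was placed and removed in the operating room are not affected.

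Confidence is high in the conflict itself but not in its consequence. The size depends on a share that the documents do not report, and the power figures are illustrations under the stated assumptions. The need for a single definition does not depend on them.

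**What to change.** Before final unblinding:

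- Replace the definition in 3.4.1.1, 10.7 and 10.8.1.1 with that of Aim 1a, and align 5.5, 10.2 and 10.10: at least one intermittent catheterization following initial IUC removal or, in a subject with no IUC, after surgery.
- State that all randomised subjects, including those with no IUC, stay in the intent-to-treat denominator.
- Have the investigators state once, without knowledge of results by arm, whether a catheterization in the operating room or PACU counts. This review does not prescribe the answer.
- State which reading the 2016 interim used.

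The cost is mostly wording. Sections 5.2 and 5.3 already collect IUC placement and removal in the operating room, straight catheterization there at the end of the case, the time of leaving the operating room, and the times of IUC removal and of each straight catheterization. They do not list where a later catheterization took place. If the investigators treat PACU separately, that must come from the medical record, including for subjects already completed; 3.4.2.3 needs the same information.

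The downside is that the event count may differ slightly from the 2016 interim. The report should disclose that the definition was reconciled after that unblinded look. The sample size and patient care are unchanged.

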4.0 SELECTION OF PATIENTS

4.1 Study population

Patients will be identified from the general surgery clinics at the University of Wisconsin Hospital and Clinics (UWHC), UW Digestive Health Center (UW DHC), The American Center (TAC), and the UW East Clinic. This includes patients who are being evaluated and worked up for surgery.

4.2 Eligibility Criteria

4.2.1 Inclusion Criteria

Patients must be 18 years of age or older, English-speaking, able to provide informed consent, and scheduled to undergo an elective, complex intra-abdominal operation with a planned postoperative inpatient stay of at least 1 night. Eligible operations will include any of the following operations approached via any operative approach (i.e. open, laparoscopic, hand-assisted laparoscopic, singleincision laparoscopic, or robotic):

- 4.2.1.1 Partial colectomy
- 4.2.1.2 Total abdominal colectomy
- 4.2.1.3 Proctocolectomy
- 4.2.1.4 Low anterior resection
- 4.2.1.5 Abdominoperineal resection
- 4.2.1.6 Restorative proctocolectomy/IPAA
- 4.2.1.7 Proctopexy (transabdominal) for prolapse
- 4.2.1.8 Intestinal stricturoplasty
- 4.2.1.9 Lysis of adhesions
- 4.2.1.10 End or diverting colostomy reversal
- 4.2.1.11 lleostomy reversal
- 4.2.1.12 Closure of enterocutaneous, enteroenteric, or enterocolic fistula
- 4.2.1.13 Partial or complete gastrectomy
- 4.2.1.14 Small bowel resection
- 4.2.1.15 Small bowel diversion/ostomy

Post-Op Urinary Retention Protocol

Version: 5.0, December 8, 2017 Page 6 of 32

- 4.2.1.16 Large bowel diversion/ostomy
- 4.2.1.17 Pancreaticoduodenectomy
- 4.2.1.18 Pancreatectomy
- 4.2.1.19 Hepatectomy
- 4.2.1.20 Gastric bypass
- 4.2.1.21 Sleeve gastrectomy
- 4.2.1.22 Nissen/Dor/Toupet fundoplication
- 4.2.1.23 Transabdominal adrenalectomy
- 4.2.1.24 Splenectomy
- 4.2.1.25 Complex abdominal wall hernia repair (i.e. Rives-Stoppa type repair, large laparoscopic ventral hernia repair)
- 4.2.1.26 Exploratory laparotomy
- 4.2.1.27 Other comparable complex intra-abdominal operations
- 4.2.2 Exclusion Criteria
 - 4.2.2.1 Less than age 18
 - 4.2.2.2 Allergy or contraindication to tamsulosin
 - 4.2.2.3 Serious sulfa allergy
 - 4.2.2.4 Current use of alpha blocker (alfuzosin, doxazosin, prazosin, silodosin, terazosin, verapamil, tamsulosin, phenoxybenzamine) or oral alpha agonist (midodrine)
 - 4.2.2.4.1 Initiation of one of these medications during the intervention phase of the study will result in subject withdrawal from the study.
 - 4.2.2.5 Current warfarin use
 - 4.2.2.6 Pre-existing indwelling urinary catheter, suprapubic catheter, or urostomy
 - 4.2.2.7 End stage renal disease or dialysis-dependence
 - 4.2.2.8 Sitting systolic blood pressure in the upper extremity of less than 100mmHg at time of eligibility screening
 - 4.2.2.9 Presence of orthostatic hypotension at the time of eligibility screening
 - 4.2.2.9.1 Orthostatic hypotension is defined as a drop in systolic blood pressure of 20mmHg from sitting to standing, or drop in diastolic BP of 10 mmHg from sitting to standing after 2-3 minutes of standing after being in a sitting position
 - 4.2.2.10 Anticipated inability to take oral medications on post-operative day #0
 - 4.2.2.11 Anticipated requirement for IUC beyond post-operative day #2
 - 4.2.2.12 Non-English speaking
 - 4.2.2.13 Pregnant or breast-feeding
 - 4.2.2.14 Unwillingness to answer all 7 questions on the IPSS survey
 - 4.2.2.15 Lacking capacity to provide informed consent

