5.3 Data collection

At the time of the pre-operative visit, following enrollment in the study, subjects will fill out the International Prostate Symptom Score (IPSS) Survey. This survey is a validated, selfadministered 7-item questionnaire that assesses obstructive lower urinary tract symptoms. Additionally, subjects will be administered a questionnaire that asks about history of prior problems with urinary retention and prior urinary tract surgeries or procedures, consisting of a total of 3 questions. Subjects may decline to answer the survey questions on the IPSS survey, but this will result in ineligibility for the trial, as IPSS score is a stratification variable for randomization. Subjects may skip the urinary tract surgery/history questions if they feel uncomfortable or embarrassed, and this will not result in exclusion from the study. Case report forms (CRFs) will be utilized to collect data prospectively during the subject's postoperative course while inpatient. This data will be collected by a study team member, and will include time of arrival and departure from the operating room, time of first void, date/time of IUC removal, date/time of first void after catheter removal, first post-void residual volume, date/time of first straight catheterization (if applicable), date/time of all subsequent straight catheterizations (if applicable), date/time of IUC replacement (if applicable), and date/time of the first two adequate voids (if applicable). Finally, subjects will be contacted by telephone 30-

40 days after the date of surgery to ask if they have been treated for a urinary tract infection since discharge from the hospital (in order to capture UTIs that are diagnosed outside of our hospital system). Additionally, data regarding adverse events will be collected using an Adverse Event Log. A study team member will make contact with the subject at two separate time points to inquire about adverse events: 1) on the day of surgery (in person, in the hospital), and 2) postoperatively via telephone call 30-40 days after surgery. Additionally, adverse events will be abstracted from the electronic medical record during the immediate postoperative period. AEs occurring following surgery up until 48 hours after discontinuing study drug will be abstracted from the subject's EMR.

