15.0 APPENDIX

ELIGIBILITY CHECKLIST

Any patient being seen in a general surgery clinic at UWHC or the UW Digestive Health Center for possible complex intra-abdominal surgery is a potential subject.

Inclusion criteria:

- □ >= 18 years of age
- □ English-speaking
- □ able to provide informed consent
- □ scheduled to undergo elective complex intra-abdominal surgery with a planned stay of at least 1 night in the hospital after surgery
- "complex intra-abdominal surgery" includes one of the following operations via ANY transabdominal approach (i.e. open, laparoscopic, hand-assist laparoscopic, single-incision laparoscopic, robotic):

- Partial colectomy
- Total abdominal colectomy
- Proctocolectomy
- Low anterior resection
- o Abdominoperineal resection
- Restorative proctocolectomy/IPAA
- Proctopexy (transabdominal) for prolapse
- Intestinal stricturoplasty
- Lysis of adhesions
- End or diverting colostomy reversal
- o lleostomy reversal
- o Closure of enterocutaneous, enteroenteric, or enterocolic fistula
- Partial or complete gastrectomy
- Small bowel resection
- Small bowel diversion/ostomy
- Large bowel diversion/ostomy
- o Pancreaticoduodenectomy
- Pancreatectomy
- Hepatectomy
- Gastric bypass
- Sleeve gastrectomy
- Nissen/Dor/Toupet fundoplication
- Transabdominal adrenalectomy
- Splenectomy
- Complex abdominal wall hernia repair (i.e. Rives-Stoppa type repair, large laparoscopic ventral hernia repair)
- Exploratory laparotomy
- o Other comparable complex intra-abdominal operation

Exclusion criteria:

- allergy or contraindication to tamsulosin
- serious sulfa allergy
- current use of an alpha blocker (alfuzosin, doxazosin, prazosin, silodosin, terazosin, verapamil, tamsulosin, phenoxybenzamine) or oral alpha agonist (midodrine)
- current warfarin use
- □ current indwelling urinary catheter, suprapubic catheter, or urostomy
- end stage renal disease or dialysis-dependent
- sitting systolic blood pressure in the upper extremity of less than 100mmHg at time of eligibility screening
- presence of orthostatic hypotension at the time of eligibility screening
 - orthostatic hypotension is defined as a drop in systolic blood pressure of 20mmHg from sitting to standing, or drop in diastolic BP of 10 mmHg from sitting to standing after 2-3 minutes of standing after being in a sitting position
- anticipated inability to take oral medications on post-operative day #0
- □ anticipated requirement for indwelling urinary catheter beyond post-operative day #2

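### The catheter exclusion leaves out patients who already empty the bladder by intermittent catheterization, although that procedure is the primary endpoint (minor)

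*Combined protocol and SAP*

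**What the plan says.** Section 4.2.2.6 excludes patients with "Pre-existing indwelling urinary catheter, suprapubic catheter, or urostomy". The Eligibility Checklist in Appendix 15.0 has the matching line "current indwelling urinary catheter, suprapubic catheter, or urostomy". The nearest other criterion, 4.2.2.11, reads "Anticipated requirement for IUC beyond post-operative day #2" and so concerns an indwelling catheter only. Criterion 4.2.2.14 requires that the seven IPSS questions be answered but excludes no score.

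The primary endpoint in 3.4.1.1, repeated in 10.7, is "Need for any intermittent catheterization after initial IUC removal". Aim 1a (3.1.1) defines postoperative retention as "need for at least a single intermittent catheterization after surgery or following the removal of IUC". Sections 3.4, 10.7 and 10.10 state no exception or adjustment for catheterization before surgery.

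Urinary history is collected after enrollment (5.3, 5.6.2) with a short "questionnaire that asks about history of prior problems with urinary retention and prior urinary tract surgeries or procedures". Subjects may skip these questions, and "this will not result in exclusion from the study". The stratification factors in 10.1 are gender, pelvic or non-pelvic surgery, and IPSS category.

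**The concern.** The exclusion covers three ways of draining the bladder that exist before surgery and omits a fourth, which is the one the primary endpoint counts. Someone who self-catheterizes, for example for chronic retention, meets no exclusion. When that patient continues the usual practice on the ward, the catheterization looks the same as a primary event.

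Such an event reflects a condition present at baseline, not a complication of surgery. On the assumption that a week of study drug does not change the habit, it adds the same amount to both arms and pulls the comparison toward no difference.

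Three further results are affected:
- The count of intermittent catheterizations (3.4.2.4) would be inflated.
- Time to first spontaneous void and first post-void residual (3.4.2.3, 3.4.2.5) may be missing for a patient who does not void.
- The Aim 2 logistic model (5.5, 10.10) has the primary endpoint as its response, so a long-standing condition would appear as predicted postoperative retention.

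**Working it through.** **Is there a route by which these patients are excluded?** I went through 4.2.1, 4.2.2 and the checklist line by line. Indwelling catheter, suprapubic catheter and urostomy are named; intermittent catheterization is not. The alpha-blocker exclusion (4.2.2.4) may remove some patients with chronic retention, but it does not name the condition. The urinary history questionnaire does not decide eligibility. So the answer is no.

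**Inputs from the documents.** Placebo rate 30%, tamsulosin rate 15%, 80% power and 134 per arm (10.2); two-sided alpha 0.05 (10.3); 1:1 allocation (10.1).

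**Reproducing the plan's sample size.** With mean rate p̄ = 0.225:

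n₀ = [1.960·√(2·0.225·0.775) + 0.842·√(0.30·0.70 + 0.15·0.85)]² / 0.15² = (1.157 + 0.489)² / 0.0225 ≈ 120.5

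With the continuity correction, n = (n₀/4)·[1 + √(1 + 4/(n₀·0.15))]² ≈ 133.5, which rounds up to 134. This matches 10.2.

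**Adding the baseline catheterizers.** Let f be the share of each arm that catheterizes intermittently before surgery. The documents do not give f, so the values below are assumptions. I also assume that all of them count as events and that everyone else keeps 30% versus 15%. Then:

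- placebo rate a = f + (1 − f)·0.30
- tamsulosin rate b = f + (1 − f)·0.15
- difference a − b = (1 − f)·0.15
- power = Φ{[(a − b) − 1/134 − 1.960·√(2p̄(1 − p̄)/134)] / √([a(1 − a) + b(1 − b)]/134)}, with p̄ = (a + b)/2

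For f = 1%: a = 0.01 + 0.99·0.30 = 0.307 and b = 0.01 + 0.99·0.15 = 0.1585. The numerator is 0.1485 − 0.00746 − 1.960·0.05163 = 0.03985 and the denominator is 0.05082. The ratio is 0.784, so power is 78.4%.

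| f (assumed) | Patients per arm (134·f) | Placebo | Tamsulosin | Difference (points) | Risk ratio | Power |
|---|---|---|---|---|---|---|
| 0 | 0 | 30.0% | 15.0% | 15.0 | 0.50 | 80.2% |
| 0.5% | 0.7 | 30.4% | 15.4% | 14.9 | 0.51 | 79.3% |
| 1% | 1.3 | 30.7% | 15.9% | 14.85 | 0.52 | 78.4% |
| 3% | 4.0 | 32.1% | 17.6% | 14.55 | 0.55 | 74.7% |
| 5% | 6.7 | 33.5% | 19.3% | 14.25 | 0.57 | 71.1% |

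Exact Fisher power agrees: 80.6% at f = 0, 78.7% at 1% and 71.3% at 5%.

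**The case against.** The strongest reply is that the problem is hypothetical and small. No prevalence is given, and nothing shows that such a patient was enrolled. At a share of 0.5%, fewer than one patient per arm is involved and power moves by less than one point. Because allocation is randomized, the error is conservative and does not undermine a positive result. All of this stands, and it is why the point is minor.

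Three stronger readings are tempting, and the documents do not support them.

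- A reader might infer that these patients are certain to be events. The endpoint is a need for catheterization, and the institutional bladder management protocol governs ward practice. Only its starting conditions appear in the text available here, so any provision for chronic catheterizers cannot be seen. Very likely is as far as the text goes; the 100% event rate above is an assumption.
- A reader might infer that the urinary questionnaire is the only step that could reveal them. Section 8.0 also provides for pre-screening of the electronic record and for a checklist completed with the patient, and 5.2 for extraction of medical and surgical history. Any of these could bring the condition to light. What is missing is a criterion that tells staff to act on it.
- A reader might infer a bias toward one arm. Randomization leaves only chance imbalance, although baseline catheterization is not a stratification factor.

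It can also be said that the 30% and 15% planning rates may already include such patients. Planned power would then be unchanged, but the misclassification would remain.

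**Conclusion.** The gap is real on the text. Patients whose usual way of emptying the bladder is the endpoint procedure are eligible, and nothing in the endpoint definition sets them apart. The consequence is dilution and misclassification. Severity is minor.

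The loss is about one power point at an assumed 0.5%, about two at 1% and between five and six at 3%. These figures assume that every such patient is an event and that the planning rates describe the remaining patients. The planned size gives 80.2% power with nobody affected, so there is little slack to absorb even a small loss. The case for a change rests mainly on its low cost and a cleaner endpoint definition.

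**What to change.** Add to 4.2.2.6 and the matching checklist line: current intermittent (self-)catheterization, including a catheterizable urinary diversion. Ask about it at formal eligibility screening, which already precedes randomization (5.6.2, 8.0), so no new visit or test is needed.

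The amendment cannot reach subjects already randomized. This is Version 5.0, and 10.5 already reports an interim result. For those subjects, identify baseline intermittent catheterization from the extracted medical history and the urinary questionnaire, without reference to treatment assignment. Keep them in the intent-to-treat analysis, and add a sensitivity analysis of the primary endpoint and of the Aim 2 model without them. Because the questionnaire may be skipped and, as described, asks about past retention and procedures, the medical history should be the main source.

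The cost is one line in two places, a few fewer eligible patients and one extra analysis.
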